3.2.2.4 Prior/Concomitant/Post-treatment Medications

Medications will be classified as prior or concomitant (but not both) according to its start/stop date. Prior medication is defined as any medication with a stop date prior to the first dose of study treatment (exclusive). Concomitant medication is defined as any medication with a stop date on or after the first dose of study treatment. Concomitant medication will also include any medication taken prior to or during study treatment that is on-going, including any treatment with a start date within 28+7 days after stopping study treatment.

Subsequent anti-cancer treatment includes therapies with a start date after the last dose of study treatment. Hence, patients starting subsequent anti-cancer treatment will no longer be on the study treatment combination, osimertinib monotherapy, or on savolitinib monotherapy.

The imputation method described in section 3.1.4.2 will be used in case of medication stop date partially missing. Completely missing stop date will not be imputed, and medication will be classified as concomitant.

All medications will be coded according to the World Health Organization Drug Dictionary Enhanced and Herbal Dictionary [WHO-DDE + HD] 2018Mar B3 format, or later version.

3.2.2.5 Electrocardiogram Changes

Electrocardiograms [ECG] will be collected centrally. Triplicate 12-lead ECGs will be obtained at Screening, weekly in Cycle 1, Day 1 in every subsequent cycle and treatment discontinuation, using an

ECG machine that automatically calculates the heart rate and measures, PR, QRS, QT, and QTcF intervals. A 28-day follow-up assessment will only be required if an on-treatment assessment was abnormal at the time of study treatment discontinuation.

Triplicate ECGs are required to support PK sampling timepoints. As such, triplicate ECGs will be required on Cycle 3 Day 1 pre-dose, at 1 hour (h), 3 h, 4 h, and 6 h post-dose to coincide with collection of blood samples for assessment of PK of osimertinib and savolitinib at this visit.

Categorical ECG interpretation (normal, abnormal) and whether clinically significant will also be provided.

Absolute and percentage change from baseline in ECG variables will be calculated for each post-baseline visit.

3.2.2.6 Vital Signs Changes

Vital signs (blood pressure [BP], pulse, temperature, and respiration rate) will be evaluated at screening, weekly during Cycle 1, Day 1 in every subsequent cycle, at treatment discontinuation, and at the 28-day follow-up visit. Weight will be assessed on Day 1 of each cycle for the first 6 cycles then every 8 weeks after; height will be assessed at screening only.

Absolute and percentage change from baseline in vital signs variables will be calculated for each post-baseline visit.

3.2.2.7 Laboratory Data

The laboratory variables will be measured at screening, weekly in Cycle 1, at every visit in subsequent cycles, and at treatment discontinuation.

Table 9 Laboratory safety variables

Clinical chemistry safety	Haematology	Urinalysis (dipstick)
S/P – Albumin	B – Haemoglobin	U – Glucose
S/P – ALT	B – Leucocyte cell count	U – Protein
S/P – AST	B – Haematocrit	U – Blood
S/P – ALP	B – Red blood cell count	U – Ketones
S/P – Bilirubin, total	B – Reticulocytes	U – Leukocyte esterase
S/P – Calcium, total	B – Absolute leucocyte differential count	
S/P – Creatinine	B – Neutrophil count	
S/P- Glucose	B – Lymphocyte count	
S/P – Magnesium	B – Eosinophil count	
S/P – Sodium	B – Platelet count	

S/P – Potassium		
S/P – Total protein		
S/P – Blood urea nitrogen (BUN) or Urea		
S/P – Lactate dehydrogenase		
S/P – Amylase		
S/P - Gamma glutamyl transferase		

ALP Alkaline phosphatase; ALT Alanine aminotransferase; AST Aspartate aminotransferase; B Blood; BUN Blood urea nitrogen; P Plasma; S Serum; U Urine.

The clinical chemistry, haematology, coagulation, and urinalysis will be performed by the local laboratory. All parameters of above will be converted to standard unit (the Système International [SI] units) when presented in summary tables and listings.

Pregnancy tests will be performed for pre-menopausal women of childbearing potential.

Corrected calcium product will be derived during creation of the reporting database using the following formula:

$$\text{Corrected calcium (mmol/L)} = \text{Total calcium(mmol/L)} + ([40 - \text{albumin(G/L)}] \times 0.02)$$

Laboratory values will be classified as low (L), normal, and high (H) according to the normal ranges. The assessment of haematology, clinical chemistry, and coagulation that deviate above or below the normal range will be classified by Common Terminology Criteria [CTC] grade (NCI CTCAE v5) taking values: Grade 0, 1, 2, 3, or 4.

Absolute and percentage change in laboratory parameters will be calculated from baseline to each post-baseline visit.

3.2.3 Patient Reported Outcome Variables

3.2.3.1 Calculation or derivation of patient reported outcome variables

3.2.3.1.1 EORTC QLQ-C30 & QLQ-LC13

Symptoms and overall quality of life will be assessed using European Organisation for Research and Treatment of Cancer Quality of Life Questionnaire-Core 30 [EORTC QLQ-C30] and Quality of Life Questionnaire-Lung Cancer 13 [QLQ-LC13].

The QLQ-C30 consists of 30 questions, which can be combined to produce 5 functional scales (Physical, Role, Cognitive, Emotional, Social), 3 symptom scales (Fatigue, Pain, Nausea/vomiting), 6 individual items (dyspnoea, insomnia, appetite loss, constipation, diarrhoea, financial difficulties) and a global measure of health status.

The QLQ-LC13 is a lung cancer specific module comprising 13 questions to assess lung cancer

symptoms (cough, haemoptysis, dyspnoea, and site-specific pain), treatment related side-effects (sore mouth, dysphagia, peripheral neuropathy, and alopecia), and pain medication; with the exception of a multi-item scale for dyspnoea, all are single items. The dyspnoea scale will only be used if all 3 items have been scored, otherwise the items are treated as single-item measures.

An outcome variable consisting of a score from 0 to 100 will be derived for each of the symptom scales/symptom items, the functional scales and the global health status/QoL scale in the QLQ-C30 and for each of the symptom scales/items in the QLQ-LC13 according to the EORTC QLQ-C30 Scoring Manual and EORTC QLQ-LC13 instructions. The scoring is done in two steps:

- 1) Calculate the raw score [RS] by taking the average of the scores for the items that contribute to the scale. The range of raw scores (RS_{range}) is the difference between the maximum and the minimum possible score (e.g. if the item score range is between 1 and 4, RS_{range} is 3).
- 2) Use a linear transformation to standardise RS to take values from 0 to 100 as follows:

$$\text{Functional scales: } (1 - \frac{(RS-1)}{RS_{range}}) \times 100$$

$$\text{Symptom scales / items / global measure of health status: } \frac{(RS-1)}{RS_{range}} \times 100$$

Higher scores on the global health status and functioning scales indicate better health status/function. Higher scores on the symptom scales indicate greater symptom burden. For each subscale, if less than 50% of the subscale items are missing, then the subscale will be divided by the number of non-missing items and multiplied by the total number of items on that subscale. If at least 50% of the items are missing, then that subscale will be treated as missing. Missing single items are treated as missing. The reason for missing questionnaires will be identified and recorded. If there is evidence that the missing data are systematic, missing values will be handled to ensure that any possible bias is minimised.

The primary PRO outcome measures will be 5 patient-reported lung cancer symptoms, namely:

- Dyspnoea (multi-item scale based on three questions: “Were you short of breath when you rested; walked; climbed stairs”) (LC13),
- Cough: one item (“How much did you cough?”) (LC13),
- Pain: one item (“Have you had pain in your chest”) (LC13).
- Fatigue (a composite score of three items: “Did you need rest; Have you felt weak; Were you tired”) (C30)
- Appetite loss: one individual item (“Have you lacked appetite”) (C30)

Changes in score compared to baseline will be evaluated. A minimum clinically meaningful change is defined as a change in the score from baseline of ≥ 10 for scales/items from the QLQ-LC13 and the QLQ-C30.

At each post-baseline assessment, change in symptoms/functioning/items from baseline will be categorised as improved, stable, or worsening as shown in Table 10.

Table 10 Visit response for QLQ-C30/QLQ-LC13 subscales

Score	Change from baseline	Visit Response
QLQ-LC13/QLQ-C30 symptom scales/items	$\geq+10$	Worsened
	≤-10	Improved
	Otherwise	Stable
QLQ-C30 functional scales and Global health status/QoL	$\geq+10$	Improved
	≤-10	Worsened
	Otherwise	Stable

Time to symptom deterioration

For each of the symptoms scales/items in EORTC QLQ-C30 and QLQ-LC13, time to symptom deterioration will be defined as the time from first dose of study treatment until the date of first clinically meaningful symptom deterioration (an increase in the score from baseline of ≥ 10) or death (by any cause) in the absence of a clinically meaningful symptom deterioration, regardless of whether the patient withdraws from study treatment or receives another anti-cancer therapy prior to symptom deterioration.

Death will be included as an event only if the death occurs within two visits of the last PRO assessment where the symptom change could be evaluated. Patients whose symptoms (as measured by EORTC QLQ-C30 and QLQ-LC13) have not shown a clinically meaningful deterioration and who are alive at the time of the analysis will be censored at the time of their last PRO assessment where the symptom could be evaluated. Also, if symptoms progress after two or more missed PRO assessment visits or the patient dies after two or more missed PRO assessment visits, the patient will be censored at the time of the last PRO assessment where the symptom could be evaluated. If a patient has no evaluable visits or does not have baseline data, they will be censored at Day 1. The population for analysis of time to symptom deterioration will include a subset of the Safety analysis set who have EORTC QLQ-LC13 or EORTC QLQ-C30 baseline scores ≤ 90 .

Symptom improvement rate

The symptom improvement rate will be defined as the number (%) of patients with two consecutive assessments which showed a clinically meaningful improvement (a decrease from baseline score ≥ 10 for EORTC QLQ-LC13 scales/items and EORTC QLQ-C30 scales/items) in that symptom from baseline. The denominator will consist of a subset of the Safety analysis set who have a baseline symptom score ≥ 10 .

Compliance rate

The compliance rate (%) and the evaluability rate (%) for EORTC QLQ-C30 and QLQ-LC13 will be calculated. This is based on:

- Received questionnaire = a questionnaire that has been received and has a completion date and at least one individual item completed.
- Expected questionnaire = a questionnaire that is expected to be completed at a scheduled assessment time, i.e. a questionnaire from a patient who has not withdrawn from the study at the scheduled assessment time.
- Evaluable questionnaire = a questionnaire with a completion date and at least one subscale that is non-missing.

The compliance rate is the number of evaluable questionnaires divided by the number of expected questionnaires, multiplied by 100. The evaluability rate is the number of evaluable questionnaires divided by the number of received questionnaires, multiplied by 100.

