- Dyspnoea (multi-item scale based on three questions: “Were you short of breath when you rested; walked; climbed stairs”) (LC13),
- Cough: one item (“How much did you cough?”) (LC13),
- Pain: one item (“Have you had pain in your chest”) (LC13).
- Fatigue (a composite score of three items: “Did you need rest; Have you felt weak; Were you tired”) (C30)
- Appetite loss: one individual item (“Have you lacked appetite”) (C30)

Definition of clinically meaningful changes

Changes in score compared to baseline will be evaluated. A minimum clinically meaningful change is defined as a change in the score from baseline of ≥ 10 for scales/items from the QLQ-LC13 and the QLQ-C30 ([Osoba et al 1998](#)).

For example, a clinically meaningful deterioration or worsening in chest pain (as assessed by QLQ-LC13) is defined as an increase in the score from baseline of ≥ 10 . A clinically meaningful improvement in fatigue (as assessed by QLQ-C30) is defined as a decrease in the score from baseline of ≥ 10 .

At each post-baseline assessment, change in symptoms/functioning from baseline will be categorised as improved, stable or worsening as shown in [Table 14](#).

Table 14 Visit Response for HRQoL and disease-related symptoms

Score	Change from baseline	Visit Response
QLQ-LC13/QLQ-C30 symptom scales/items	≥+10	Worsened
	≤-10	Improved
	Otherwise	Stable
QLQ-C30 functional scales and Global health status/QoL	≥+10	Improved
	≤-10	Worsened
	Otherwise	Stable

Time to symptom deterioration

Time to deterioration in symptoms, functioning and global health status/QoL will be evaluated, more details will be specified in the SAP.

Symptom improvement rate

Improvement in symptoms, functioning and global health status/QoL will be evaluated, more details will be specified in the SAP.

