4.2.2.6 Secondary Endpoint – EORTC QLQ-C30 and QLQ-LC13

4.2.2.6.1 Target Population Analysis Set

For EORTC QLC-C30 and QLQ-LC13, respectively, the observed values and change from baseline of functional/symptom scales, the individual items and the global health status scores will be summarised over time using descriptive statistics.

The improvement rate, i.e. proportion of patients with improvements, and 95% Clopper-Pearson CIs for each scale/item score will be summarised. The improvement rate is based on the number of patients who have a baseline individual score ≥ 10 .

Time to deterioration for the symptom scales and the individual items will be summarised using Kaplan-Meier methodology. Median and quartile time to deterioration and the percentage of patients being free of deterioration at selected timepoints, along with the 95% CI, will be presented. The population for analysis of time to symptom deterioration will include a subset of the Safety analysis set who have EORTC QLQ-LC13 or EORTC QLQ-C30 baseline scores ≤ 90 .

The compliance and evaluable rate (%) will be presented together with the number of evaluable, received and expected questionnaires at each timepoint.

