6 CHANGES OF ANALYSIS FROM PROTOCOL

Although not specified in the current CSP version 7.0, Change in tumour size by investigator assessment in accordance with RECIST 1.1, best percentage change in TL tumour size, CNS ORR and CNS DoR by BICR assessments in accordance with RECIST 1.1 have been considered of interest for this study and will be explored.

Moreover, OS and PFS timepoints will be extended compared to CSP version 7.0 requirements.

DoR, PFS by investigator assessment in accordance with RECIST 1.1 will be assessed for CAS. Although present in CSP version 7.0 endpoints, DoR and PFS by ≥ 3 line of treatment will not be explored in this statistical analysis. Baseline assessments related to RECIST 1.1 will not follow CSP version 7.0 definition where 28 days window is required.

Finally, IUO grade status has been introduced. At this regard, ORR, DoR, PFS by investigator will be assessed in accordance with RECIST 1.1 using retrospective IUO grade MET testing on TPAS, SAF and CAS.

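### The SAP's missing-item rule does not fit its own mean-based QLQ raw score, and the SAP omits, without declaring it, the protocol's time to deterioration in functioning and global health

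*SAP*

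**What the plan says.** **Scoring.** SAP 3.2.3.1.1 sets out two steps. Step 1: "Calculate the raw score [RS] by taking the average of the scores for the items that contribute to the scale". Step 2 is a linear transformation meant to give values from 0 to 100. The raw-score range is 3 in the SAP's example, "if the item score range is between 1 and 4". The section then deals with partly answered scales. When fewer than half of the items are missing, "the subscale will be divided by the number of non-missing items and multiplied by the total number of items on that subscale"; when half or more are missing, the scale is set to missing. Protocol 9.4.3.3 carries the same missing-item rule but gives no raw-score formula. Both documents use the LC13 dyspnoea scale only when all three of its items are answered.

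**Time to deterioration.** Protocol 9.4.3.3 states: "Time to deterioration in symptoms, functioning and global health status/QoL will be evaluated, more details will be specified in the SAP". SAP 3.2.3.1.1 supplies those details for symptoms only: "For each of the symptoms scales/items in EORTC QLQ-C30 and QLQ-LC13, time to symptom deterioration will be defined as". The event is a "clinically meaningful symptom deterioration (an increase in the score from baseline of ≥ 10" points, or death under a two-visit rule, in patients whose baseline score is at most 90. SAP 4.2.2.6.1 matches that scope: "Time to deterioration for the symptom scales and the individual items will be summarised using" Kaplan-Meier methods. SAP Section 6 lists departures from the protocol, including a dropped analysis of DoR and PFS by "line of treatment will not be explored in this statistical analysis", but says nothing about time to deterioration.

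**The concern.** Dividing by the answered items and multiplying by all items estimates a full-scale total. The SAP's transformation needs a mean. If the rule is programmed as it reads, a skipped item changes the score by itself and can push it outside 0-100. The affected scores feed the mean change from baseline, the improved/stable/worsened visit categories, the improvement rate and the time to deterioration. Partial completion is foreseen, because the SAP counts a questionnaire as received with only one item completed.

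On the second matter, the protocol left the details of a three-domain analysis to the SAP, and the SAP delivers one domain. Nobody reading the SAP's own list of changes would learn that functioning and global health had been left out.

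**Working it through.** **Inputs** (SAP 3.2.3.1.1)
- RS = mean of the items.
- Symptom score = (RS − 1)/range × 100. Functional score = (1 − (RS − 1)/range) × 100.
- Fatigue has three items. I take them as scored 1 to 4, as in the SAP's example, so range = 3.
- Clinically meaningful change: 10 points.

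**Step 1: complete data.** All items 1 gives (1 − 1)/3 × 100 = 0. All items 4 gives (4 − 1)/3 × 100 = 100. The stated 0-100 range is reproduced.

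**Step 2: where the rule applies.** One of three items missing is 33%, so fatigue is prorated. One of two is 50%, so a two-item scale is set to missing. Single items are not prorated, and LC13 dyspnoea needs all three items. Of the five primary PRO measures (dyspnoea, cough, chest pain, fatigue, appetite loss), only fatigue is exposed.

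**Step 3: fatigue answered 2, 2, missing.** The complete pattern 2, 2, 2 scores (2 − 1)/3 × 100 = 33.3. The rule can be read in four ways:

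| Reading | Calculation | Score | False change |
|---|---|---|---|
| A: answered mean × 3/2 used as RS | RS = 3; (3 − 1)/3 × 100 | 66.7 | +33.3 |
| B: answered sum / 2 × 3 used as RS | RS = 6; (6 − 1)/3 × 100 | 166.7 | +133.3 |
| C: transformed score × 3/2 | 33.3 × 1.5 | 50.0 | +16.7 |
| D: prorated sum divided again by 3 | RS = 6/3 = 2 | 33.3 | 0 |

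A, B and C each exceed 10 points, so a patient whose answers have not changed is classed as worsened and has a deterioration event. If the item is missing at baseline instead, the error runs the other way and shows as improvement.

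**Step 4: all 16 answer patterns for fatigue with one item missing**

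| Reading | Range of scores | Patterns outside 0-100 |
|---|---|---|
| A | 16.7 to 166.7 | 6 of 16 |
| B | 66.7 to 366.7 | 15 of 16 |
| C | 0 to 150 | 3 of 16 |
| D | 0 to 100 | 0 of 16 |

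**Step 5: functional scales.** The documents give no item counts, so these are assumptions. Under reading A the lowest possible score is −44.4 (four items, one missing), −33.3 (five items, one missing) or −88.9 (five items, two missing).

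**Step 6: time to deterioration, side by side.**

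| Domain | Protocol 9.4.3.3 | SAP 3.2.3.1.1 and 4.2.2.6.1 |
|---|---|---|
| Symptom scales and items | promised | defined and summarised |
| Five functional scales | promised | absent |
| Global health status/QoL | promised | absent |

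The count is 5 + 1 = 6 scales. The SAP's definition cannot simply be stretched to them. Its event is a rise of 10 or more, which SAP Table 10 classes as improvement for functional scales and global health. Its baseline limit of 90 leaves room for a rise of 10 (100 − 90), whereas these scales need room for a fall.

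**The case against.** The best defence on scoring is that the SAP also tells the programmer to follow the EORTC scoring manual and to produce a score from 0 to 100. Reading D is the only one of the four that always stays in that range. It also arises if one averages over all three items, counting the missing one as nothing, before prorating. Correct programming is therefore likely. That limits the practical risk but does not remove the contradiction: the SAP spells out its own steps, and the step that rescues them is not among them.

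On time to deterioration, the defence is that the listed secondary endpoint is mean change from baseline. SAP 4.2.2.6.1 keeps that for the functional scales and global health, with improvement rates, and Table 10 classifies their visits. All five primary PRO measures are symptoms, and what is missing is a descriptive summary with no test attached. All of that stands. It bears on the weight of the point, not on whether the change should have been declared.

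A reader might go further in four ways that the documents do not support:
- **That the rule always gives impossible scores.** It does not. Under A and C most fatigue patterns stay in range, and B, the source of the largest values, is only one reading.
- **That LC13 dyspnoea is caught by conflicting rules.** The specific all-three-items rule is already in both documents and governs.
- **That a definite error can be quoted for physical functioning.** Neither document says how many items that scale has.
- **That the HRQoL secondary endpoint has been dropped.** It has not.

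**Conclusion.** Both parts hold, within limits.

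The missing-item rule is wrong as written for a mean-based raw score. For fatigue with one item missing, the worked pattern is misscored by 16.7, 33.3 or 133.3 points under the three readings that add nothing to the text, each beyond the 10-point threshold. This rests on items scored 1 to 4. It affects only scales of three or more items with fewer than half missing. How often that will happen cannot be judged from the documents, so the effect on group summaries is not quantified.

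The omission of time to deterioration for six scales is an undeclared departure from Protocol 9.4.3.3. Its consequence is the loss of one descriptive analysis.

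Neither part touches the primary endpoints. Both should be corrected because the remedy is cheap and the scoring sentence, if followed literally, gives wrong data.

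**What to change.** 1. **Scoring.** In SAP 3.2.3.1.1, replace the proration sentence with: *RS is the mean of the answered items when fewer than 50% are missing.* Correct the same sentence in Protocol 9.4.3.3. With this change all 16 fatigue patterns stay within 0-100, and 2, 2, missing scores 33.3. LC13 dyspnoea stays under its existing all-three-items rule.
2. **Time to deterioration.** Either define it for the five functional scales and global health status/QoL as the first fall from baseline of at least 10, or death under the existing two-visit rule, in patients with a baseline score of at least 10, and add it to SAP 4.2.2.6; or declare the omission in SAP Section 6.

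The first change costs wording and a check of the scoring program. The second costs either Kaplan-Meier tables for six scales from data already collected, or one sentence in Section 6.

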PK sampling ^{n,o}			X ^o				Day 1 of Cycles 2, 3 and 6 ^o	Day 1 of Cycle 11 ^o					8.5.1

Visit	Pre-screening	Screening	Treatment Period				Follow-up ^a				Details in CSP section	
			Cycle 1 (28-day cycle)		Cycles 2 to 6 (28-day cycle)	Cycle 7 onwards (28-day cycle)	Treatment Discontinuation Visit	28-day Follow-up Visit ^b	Progression Follow-up ^c	Survival Follow up		
Week (Day 1 of)	NA	-4 to 0	1 to 4		5 to 24	25 onwards						
Study Day		-28 to -1	1 to 28		29 to 168	169 onwards						
Day of cycle	NA		1	8	15	22	1					
Visit window			±1 day		±3 days	±3 days	Within 7 days of the final dose of the last IP	±7 days	±7 days	± 7 days		
Efficacy measurements												
Tumour imaging (RECIST Version 1.1) ^p		X ^q	Q6W (±7 days) up to 24 weeks, then every Q8W (±7 days) until objective disease progression relative to randomisation (patients recruited under CSP v7.0) or the first dose of treatment (patients recruited prior to CSP v7.0)								8.1	
EORTC QLQ-C30		X	Q4W (±2 days) relative to randomisation (patients recruited under CSP v7.0) or the first dose of treatment (patients recruited prior to CSP v7.0) ^r				X ^s				8.1.2.1	
QLQ-LC13		X	Weekly (±2 days) in Cycles 1 and 2 and then Q4W (±2 days) relative to randomisation (patients recruited under CSP v7.0) or the first dose of treatment from Cycle 3 onwards (patients recruited prior to CSP v7.0) ^r				X ^s				8.1.2.1	
PGIS		X	Q8W (±2 days) relative to randomisation (patients recruited under CSP v7.0) or the first dose of treatment (patients recruited prior to CSP v7.0) ^r				X ^s				8.1.2.2	
PRO-CTCAE		X	Weekly (±2 days) in Cycles 1 and 2 and then Q4W (±2 days) relative to randomisation (patients recruited under CSP v7.0) or the first dose of treatment (patients recruited prior to CSP v7.0) from Cycle 3 onwards ^s				X ^s				8.1.2.3	

Visit	Pre-screening	Screening	Treatment Period						Follow-up ^a				Details in CSP section
			Cycle 1 (28-day cycle)			Cycles 2 to 6 (28-day cycle)	Cycle 7 onwards (28-day cycle)	Treatment Discontinuation Visit	28-day Follow-up Visit ^b	Progression Follow-up ^c	Survival Follow up		
Week (Day 1 of)	NA	-4 to 0	1 to 4			5 to 24	25 onwards						
Study Day		-28 to -1	1 to 28			29 to 168	169 onwards						
Day of cycle	NA		1	8	15	22	1	1					
Visit window			±1 day			±3 days	±3 days	Within 7 days of the final dose of the last IP	±7 days	±7 days	± 7 days		

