3.1.3 Time Windows

The date of first dose of study treatment will be considered Day 1, and the day before the first dose of study treatment will be Day -1. Relative days will be calculated as follows:

For days on or after the first dose of study treatment:

Date of assessment – Date of first dose of study treatment +1.

For days before the first dose of study treatment:

Date of assessment – Date of first dose of study treatment.

For analyses of efficacy variables for patients enrolled under CSP version 7.0, the date of randomisation will be considered Day 1, and the day before date of randomisation will be Day -1. Relative days will be calculated as follows:

For days on or after the randomisation date:

Date of assessment – Date of randomisation +1.

For days before the randomisation date:

Date of assessment – Date of randomisation.

For non-efficacy analysis, the study day is still relative to first dosing date of study treatment.

Study days will only be calculated for complete assessment dates (i.e. partial dates will have missing study day).

The time from last dose of treatment to death will be derived for complete dates as follows:

Date of death – Date of last dose of treatment

For the purpose of the statistical analysis and if not otherwise specified, all the variables (primary, secondary and exploratory variables) will be assigned to the visit/assessment timepoint in which they were collected depending on the following analysis time windows in Table 5. Where appropriate, the window for assessment days following baseline will be constructed in such a way that the upper limit of the interval falls halfway between the two timepoints.

Table 5 Time Windows

Cycle	Week	Study Day	Cycle Day	Study Day window for weekly assessments	Cycle Day window for weekly assessments	Cycle Day window for Cycle Day 1 assessments (from Cycle 2 and onwards)	Study Day window for assessments scheduled every 4 weeks [b]	Study Day window for assessments scheduled every 6 weeks	Cycle Day window for liver function tests (ALT, AST, ALP and total bilirubin)	Cycle Day window for safety laboratory assessments (other than liver function tests)
		-1	-1	-28 to -1	-1	-1	-1	-1	-1	-1
1	1	1 [a]	C1D1	1	C1D1	C1D1	1	1	C1D1	C1D1
1	2	8	C1D8	2-11	C1D2- C1D11	C1D2- C1D11	2-42	2-63	C1D8	C1D8
1	3	15	C1D15	12-18	C1D12- C1D18	C1D12- C1D18			C1D15	C1D15
1	4	22	C1D22	19-25	C1D19- C1D25	C1D19- C1D25			C1D22	C1D22
2	5	29	C2D1	26-32	C1D26- C2D4	C1D26-			C2D1	C2D1 [d]

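### The symptom improvement rate sets no minimum time between its two scores, so weekly QLQ-LC13 symptoms qualify more easily than four-weekly QLQ-C30 symptoms and the rates are not comparable

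*SAP*

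**What the plan says.** SAP 3.2.3.1.1 gives the numerator as the "number (%) of patients with two consecutive assessments which showed a clinically meaningful improvement", meaning a fall of at least 10 points. The threshold comes from the same section: "A minimum clinically meaningful change is defined as a change in the score from baseline of" 10 points or more, on either instrument. "The denominator will consist of a subset of the Safety analysis set who have a baseline symptom score" of at least 10. No interval between the two assessments is stated. SAP 4.2.2.6.1 adds a Clopper-Pearson interval for each scale or item but no timing rule. Protocol 9.4.3.3 leaves the details to the SAP.

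The instruments follow different calendars in the protocol's schedule of activities (1.1, Table 1):

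- QLQ-LC13: "Weekly (±2 days) in Cycles 1 and 2 and then Q4W (±2 days) relative to randomisation" for version 7.0 patients, or to first dose for earlier ones.
- QLQ-C30: "Q4W (±2 days) relative to randomisation (patients recruited under CSP v7.0", or first dose for earlier ones), throughout.

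SAP 3.1.3, Table 5, has its own column, "Study Day window for weekly assessments", and no rule folds weekly LC13 data into 4-weekly visits.

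The SAP also states: "The primary PRO outcome measures will be 5 patient-reported lung cancer symptoms". Dyspnoea, cough and chest pain come from LC13; fatigue and appetite loss come from C30.

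**The concern.** Confirmation is counted in questionnaires, not in time. One statistic, reported under one name for five headline symptoms, therefore carries two standards. Three symptoms have more chances to qualify, and the early chances are only about a week apart.

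The 10-point threshold gives little protection against answer noise. A four-level single item scores in steps of 100/3 = 33 points. On a three-item scale such as dyspnoea, one category on one item moves the score by 33/3 = 11 points. Restricting the denominator to patients with some symptom at baseline also favours regression to the mean. The two-assessment requirement is what has to screen out chance improvement, and it is weaker for LC13 in Cycles 1 and 2. An early qualifying pair makes the patient a responder whatever follows.

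The SAP deals with this problem elsewhere. Tumour response needs repeat imaging at least 4 weeks later (3.2.1.1.2), and two missed scans are converted into weeks because the scan interval changes (3.2.1.1.5). The improvement rate has no equivalent.

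At stake is how the absolute LC13 rates are read, and whether a higher rate for cough than for fatigue reflects the drug or the calendar.

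**Working it through.** The documents give no expected improvement rate, so there is no plan figure to reproduce.

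**1. Gaps and pairs (from the documents).** Nominal post-baseline days to Week 24 (day 169):

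- LC13: 8, 15, 22, 29, 36, 43, 50, 57, 85, 113, 141, 169. That is 12 assessments and 11 consecutive pairs, 7 of them one week apart and 4 of them four weeks apart.
- C30: 29, 57, 85, 113, 141, 169. That is 6 assessments and 5 pairs, all four weeks apart.

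With ±2 days on each visit, the shortest LC13 gap is 7 ± 4 = 3 to 11 days, and the C30 gap is 28 ± 4 = 24 to 32 days.

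**2. Effect of the number of pairs alone.** Suppose each assessment looks improved independently with probability p (assumed). Let q(n) be the chance of no two successive improved scores in n assessments: q(0) = q(1) = 1 and q(n) = (1−p)·q(n−1) + p(1−p)·q(n−2). The chance of qualifying is 1 − q(n).

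| p | LC13, n = 12 | C30, n = 6 |
|---|---|---|
| 0.1 | 9.7% | 4.6% |
| 0.2 | 32.2% | 16.4% |
| 0.3 | 57.4% | 32.7% |

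**3. Correlated scores.** The same four-level item was simulated on both schedules. Assumptions: stable patient level SD 0.8; assessment noise SD 0.5 or 0.7; weekly noise correlation 0, 0.3, 0.5 or 0.7; cut-points −0.5, 0.7 and 1.8; baseline score at least 10; no dropout; 200,000 simulated patients per setting. Benefit is a constant downward shift on the latent scale. Rates to Week 24, with ranges over the settings:

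| True shift | LC13 schedule | C30 schedule | Gap (points) | LC13 with 21-day rule |
|---|---|---|---|---|
| 0, noise 0.5 | 44.1–47.7% | 33.0–35.2% | 11.1–13.7 | 32.2–37.4% |
| 0, noise 0.7 | 57.3–60.7% | 44.1–46.1% | 13.2–16.1 | 43.3–48.8% |
| 0.6 | 80.6–86.5% | 70.2–74.7% | 10.4–12.6 | 70.1–78.1% |
| 1.2 | 96.9–98.1% | 92.1–94.1% | 3.6–5.2 | 92.5–95.7% |

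**4. A second model.** With cut-points −0.5, 0.5 and 1.3, stable between-patient variance share 0.3–0.9 and weekly correlation 0–0.8, no true change gives 36–70% on the LC13 schedule against 25–57% on the C30 schedule. The gap is about 10–17 points across that model's settings, including shifts of 0.3 and 0.6 SD. The direction was the same in every setting of both models.

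**The case against.** The strongest reply is that little depends on this rate. The declared endpoint is mean change from baseline in the two questionnaires (SAP section 1, Table 1), which does not use the two-assessment rule. The improvement rate has a confidence interval but no hypothesis, test or decision, and no planned analysis compares LC13 symptoms with C30 symptoms. Scores and changes are also summarised over time, and each visit is classed as improved, stable or worsened, so a reader could see an early gain fade. All of this stands, and it limits the weight of the point. It does not remove the difference in definition.

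The percentages are also open to challenge. Noise, cut-points and absence of dropout are assumed, and no true change gives the widest gaps in the first model. This too stands. The pair counts and intervals do not depend on those assumptions.

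A reader might infer more than the documents support:

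- *That fatigue and appetite loss must stay improved for four weeks.* They must be improved at two visits about 28 days apart; nothing is measured between.
- *That the SAP presents the rate as sustained or confirmed benefit.* It uses neither word for this rate.
- *That comparisons between regimens are biased.* Every regimen follows the same questionnaire schedule. Protocol 9.4.3.3 also plans these summaries in the CAS, which SAP 4.2.2.6 does not carry through, but both randomised arms would share the schedule as well.
- *That LC13 rates must be higher.* A patient improved at days 29 and 57, but never at two adjacent weekly assessments, qualifies on the C30 schedule and can fail on LC13. Higher LC13 rates are likely, not certain.
- *That the contrast at Week 8 (7 pairs against 1) measures the distortion.* The SAP sets no Week 8 rate. Any pair during collection counts, and from Cycle 3 both instruments are 4-weekly.

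**Conclusion.** The point holds for one descriptive supporting summary. Followed exactly, the plan gives three of the five headline symptoms an easier route to improvement than the other two, so LC13 and C30 rates cannot be read side by side, and the absolute LC13 rates are likely to be raised by the schedule.

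The intervals (about 7 against 28 days) and the pair counts (11 against 5 by Week 24) come from the documents. The effect on the rate rests on the assumptions above: about 11–16 points at Week 24 with no true change, 10–13 with a moderate benefit and 3–5 with a large one. Week 24 is a convenient horizon for the calculation, not one the SAP sets. Dropout was not modelled and could alter the gap. The mean-change endpoint and comparisons between dosing regimens are unaffected. The change is worth making because it is cheap, not because a main conclusion depends on it.

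**What to change.** Amend SAP 3.2.3.1.1 and 4.2.2.6.1 in one of two ways.

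1. For both instruments, count a patient as improved only if two scores at least 21 days apart each show a fall of 10 points or more, with no non-improved assessment between them. A 21-day minimum sits below the shortest in-window C30 gap (24 days), so no on-schedule C30 pair is lost; a 28-day minimum would reject some. In the first model above with no true change, this brings the LC13 rate to 32–49%, against 33–46% for C30. It does not make the standards identical: in Cycles 1 and 2 an LC13 patient nominally needs four successive improved weekly scores.
2. Derive LC13 improvement from the 4-weekly time points only, so that both instruments use one schedule and one rule. This leaves the weekly LC13 data out of this summary, though they remain in the summaries over time.

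Either way the cost is a sentence in the SAP and reprogramming, with no new data or visits. Reported LC13 improvement rates will be lower.
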